8.3 Protocol Deviations

The investigator is not allowed to deviate from the protocol except under emergency circumstances to protect the rights, safety and well-being of the subjects. Such deviation shall be documented and reported to the Sponsor and the IRB as soon as possible in accordance with 21 CFR 812.150.

The procedure for recording and reporting protocol deviations shall be via a Protocol Deviation form. Analysis of protocol deviations shall be undertaken by the Sponsor and reported to the IRBs per local requirements.

9. Study Completion

9.1 Completed Subjects

Once the 6-month post-activation visit is completed, the subject will be deemed complete and will continue to receive standard clinical follow-up care at their cochlear implant facility after the study.

9.2 Discontinued Subjects

Any subject may voluntarily discontinue the study at any time without prejudice. The Investigator may discontinue a subject from the study at any time if (s)he considers that remaining in the study compromises the subject's health or the subject is not sufficiently cooperative. In either event, the reason(s) for discontinuation should be

recorded on a study withdrawal form, provided as part of the case report form packet for the study. Possible reasons for study discontinuation include the following:

- AE necessitating discontinuation from the study
- The subject is lost to follow-up
- Voluntary decision to withdraw consent made by the subject
- Investigator decision
- Other reason

In the case of a subject lost-to-follow-up, the Investigator must attempt to contact the subject (or relative/family contact) by phone, email, or letter at least three times. If attempts are unsuccessful, the 'subject withdrawal' form is to be completed in the study file and reported to the Sponsor and, as appropriate, to the IRB.

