Study Overview	
The clinical investigation is evaluating a new clinical model in a group of newly implanted subjects who have already been consented to CI surgery.
 
This randomized multi-center study will investigate a new model (Group A) based on outcome evidence, a standardized programming and testing method that utilizes artificial intelligence and will be compared to a traditional clinical model (Group B).

Primary Objective	To evaluate the total amount of clinical time as defined by number and duration of visits in a new model (Group A) compared to a traditional clinical care schedule (Group B)
Secondary Objectives	
 1. To compare speech perception in quiet as measured on CNC words in the implanted ear. 2. To compare subject hearing outcome satisfaction on the SSQ-12 between the two models. 3. To compare device and accessory use of subjects as measured by a device use questionnaire and datalogging between the two models. 4. To compare clinician satisfaction between the models through a questionnaire. 5. To compare speech perception in noise as measured on AzBio +10 S/N in their everyday listening situation using

	the subjects preferred noise program and accessory if appropriate.
Primary Endpoint	Reduction in the overall number of minutes of cochlear implant appointments over the first 6 months post activation in the new model (Group A) compared to the traditional model (Group B).
Secondary Endpoints	
 1. Speech perception on CNC at 3 and 6 months post activation will be the same or better in the new model group compared to the traditional model. 2. Subjective hearing outcome satisfaction on the SSQ-12 at 6 months post activation will be the same or better in the new model group compared to the traditional model. 3. Device and accessory use will be the same or better at 6 months of device use with the new model compared to the traditional model as measured by a device use questionnaire and datalogging. 4. Clinician satisfaction will be the same or better with the new model when compared to the traditional model at the 6-month interval. 5. Speech perception on Az-Bio +10 S/N at 6 months post activation in the subjects everyday listening condition will be better than the pre-operative score.

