The clinical investigation is evaluating a new clinical process in a group of newly implanted subjects.

The new model (Group A) that uses a prescriptive method to deliver CI care in newly implanted adults will be compared to a control method defined as the clinics existing or (Group B) traditional model (i.e. programming, outcome testing completed in a sound booth and materials used for device counseling). The new clinical process standardizes the care model through clinical outcomes, AI based programming, test battery completed through direct connect and tools and materials used for counselling. The goal is to reduce the total amount of clinical time as defined by number and duration of visits compared to the clinics traditional model without compromising clinical outcomes or patient satisfaction.

Group A Study participants will be evaluated during the switch on ,1-month, 3-month and 6-month post op visit. In addition, sound processor and accessory usage data will be collected as well as psychophysical tests completed as part of the clinical decision support tool. Outcome measures will be collected at 3 and 6 months post activation. Total time of the appointment will be collected for each visit using a timer. Programming will be calculated from the CDX file which includes a time stamp. Other activities (accessories, device use, counseling etc.) will be estimated based on subtracting programming time from the total time of the sessions.

- Total time of appointment:
 - Timer will be started when the professional and subject are seated in the consultation room to end the session.
- Programming time
 - Will be extracted from the CDX file based on the time stamps within the session file.

- Other activities (accessories, device use, counseling etc.)
 - Will be estimated based on subtracting programming time from the total time of the sessions.
 - Note: Data entry or forms associated with data collection are not included in the total time of the appointment

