5.5 Post-operative Procedure

5.5.1 Initial Activation of Sound (Switch-on)

At the initial activation appointment, the following procedures will be completed:

- New Model (Group A):
 - Creation of AutoMAPs with AI
 - Self-directed device use using study materials and video conference call with Cochlear Recipient Services
 - Clinician reported Materials/Tools questionnaire
 - An anonymized .cdx file will be provided to the study sponsor
 - Subject Service Satisfaction Survey
- Traditional Model (Group B):
 - Programming and counselling as defined by Center
 - Complete Clinician reported Materials/Tools questionnaire
 - An anonymized .cdx file will be provided to the study sponsor
 - Subject Service Satisfaction Survey

5.5.2 1-2 weeks Post Activation

- Traditional Model (Group B)
 - Programming and/or counselling as defined by Center
 - An anonymized .cdx file will be provided to the study sponsor

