10.3 Missing Data

All efforts will be put forth to ensure near complete follow-up, with focus on the assessment of the primary outcome and occurrence of adverse events. Regular reminders of subject follow-up due dates will be provided to participating centers to facilitate scheduling of follow-up visits.

11. Risk Benefit Statement

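### Section 9.2 lets an investigator who can know the arm remove a randomised subject from the whole study for poor cooperation, with no continued data collection, so removals can bias the 6-month time comparison in either direction

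*Protocol*

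**What the plan says.** Protocol section 9.2 gives two grounds on which the investigator may discontinue a subject from the study at any time: "remaining in the study compromises the subject's health or the subject is not sufficiently cooperative". It does not define cooperation, and its list of possible reasons also includes "Investigator decision" without qualification. The reason must be "recorded on a study withdrawal form, provided as part of the case report form packet for the study". Apart from the contact attempts for subjects lost to follow-up, 9.2 asks for nothing more.

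The synopsis sets the primary endpoint as "Reduction in the overall number of minutes of cochlear implant appointments over the first 6 months post activation", Group A against Group B. It describes the design in these terms: "This randomized multi-center study will investigate a new model (Group A) based on outcome evidence". Section 4 has the new model "compared to a control method defined as the clinics existing or (Group B) traditional model". No blinding is described.

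Section 10.2 names the ITT population for adverse event reporting and restricts the completed-case and per-protocol populations to subjects who completed per the protocol. Section 10.3 sets an aim: "All efforts will be put forth to ensure near complete follow-up, with focus on the assessment of the primary outcome". The means it names is reminders to centres about due dates. Section 6 refers the analysis to a separate SAP, which is not at hand.

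**The concern.** The endpoint is a running total. A subject who leaves early has no complete 6-month total, whatever analysis is later chosen. From the visit tables in section 7, a Group A subject removed after the 1-month visit has 2 of 4 scheduled timed visits on record, and a Group B subject has 3 of 5. Both lose the 3- and 6-month CNC scores and the 6-month SSQ-12 and AzBio.

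The loss need not be random. The decision is made after randomisation, on an undefined judgement, by someone who can know the arm. Cooperation also means different things in the two arms. Group A receives a self-learning packet and instructions for arranging a support call (5.4.3), and at switch-on its programme includes "Self-directed device use using study materials and video conference call with Cochlear Recipient Services" (5.5.1). Group B is counselled as the centre defines and has a further visit at 1-2 weeks (5.5.2). If a judgement of poor cooperation is related to clinic time, and differently so by arm, the subjects who remain are no longer the groups that were randomised.

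An SAP can choose analysis sets and missing-data methods, but it cannot recover minutes that nobody timed. That part belongs to the protocol.

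**Working it through.** **No figure to reproduce.** The protocol gives no SD, effect size, alpha, power, allocation ratio or dropout rate. What follows is an illustration in SD units of total minutes.

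**Inputs.** Total sample 35 to 50 (synopsis). Assumed: 1:1 allocation (17 v 18 and 25 v 25), normally distributed totals, no true difference, two-sided t-test at 0.05, removed subjects left out of the comparison, and *k* removals in Group A with none in Group B. Each scenario was simulated 40,000 times.

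**Formula.** If *k* of *n* subjects are removed and they average *r* SD above the arm mean, the mean of those who remain shifts by −*k*·*r*/(*n*−*k*).

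**Results.** Each cell gives the shift in A minus B in SD, then the chance of a significant result favouring Group A. With no removals that chance is 2.6% (35 subjects) and 2.4% (50 subjects).

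| Total | *k* | Highest-time removed | Random from upper half | Lowest-time removed |
|---|---|---|---|---|
| 35 | 1 | −0.11; 5.5% | −0.05; 3.4% | +0.11; 1.3% |
| 35 | 2 | −0.21; 9.5% | −0.11; 4.6% | +0.21; 0.7% |
| 35 | 3 | −0.30; 14.9% | −0.18; 6.4% | +0.29; 0.3% |
| 50 | 1 | −0.08; 4.9% | −0.03; 3.3% | +0.08; 1.4% |
| 50 | 2 | −0.15; 8.7% | −0.07; 4.2% | +0.15; 0.9% |
| 50 | 3 | −0.22; 13.1% | −0.11; 5.5% | +0.22; 0.4% |

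**Reading the table with the formula.** At *n* = 17 and *k* = 2, a shift of −0.207 means *r* = 0.207 × 15/2 = 1.55 SD, so the two removed subjects average about one and a half SD above their arm. In the upper-half scenario with *k* = 1, *r* = 0.050 × 16 = 0.80 SD. A reader who expects weaker selection can insert a smaller *r*.

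**Direction.** The last column reverses the sign when low-time Group A subjects go. By symmetry, removing high-time Group B subjects also works against Group A.

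**Scale.** The difference detectable with 80% power is (1.960 + 0.842) × √(2/*n*): 0.96 SD at 17 per arm and 0.79 SD at 25. The largest worst-case shifts are 0.30/0.96 = 31% and 0.22/0.79 = 28% of those.

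**The case against.** The strongest reply is that this is a routine discontinuation clause with safeguards around it. Section 4.4 already excludes people unwilling or unable to comply, every removal needs a recorded reason, and an imbalance between arms would be visible. This is fair and makes frequent removals less likely. It does not replace the lost data.

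Several stronger readings are tempting, and the text does not support them.

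- *The clause favours Group A.* It covers both arms. Uncooperative subjects may miss visits and use less time, and Group B has an extra scheduled visit at which to fall short. No passage treats skipped self-learning as poor cooperation.
- *A truncated total will be counted as a saving.* How an incomplete total is analysed is for the SAP. Section 10.2 does not say that the primary analysis uses completers.
- *Section 9.2 contradicts 10.3.* Section 10.3 states an aim. The two are in tension, but both can stand.
- *One clinician delivers both models and judges cooperation.* The protocol does not say so. That the investigator can know the arm is an inference from visibly different care and the absence of any blinding.
- *The protocol says that collection stops.* It does not say so in words. This is the ordinary meaning of discontinuation from the study where no later collection is provided for.

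It is also fair that two or three removals, all from the top of Group A and none from Group B, is an extreme case.

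**Conclusion.** The point holds as a weakness in retention. Section 9.2 leaves an undefined ground for removal after randomisation in the hands of someone who can know the arm, merges stopping the model with leaving the study, and provides for no later collection of a cumulative endpoint. The comparison can be biased, and the direction cannot be told from the documents.

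The shift is about 0.15 to 0.30 SD in the worst case (2 or 3 highest-time Group A subjects removed) and about 0.03 to 0.18 SD under weaker selection (1 to 3 at random from the upper half). It is of similar size with the opposite sign if low-time Group A subjects go. These figures rest on assumed normality, 1:1 allocation and a comparison without the removed subjects. The protocol gives no SD, so no conversion to minutes is offered. The number of removals is also unknown; if there are none, the problem does not arise. The wording should be amended, but it does not invalidate the design.

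**What to change.** Add to section 9.2 that poor cooperation is recorded as a protocol deviation, and that stopping the assigned model is recorded as a change of model; neither is by itself withdrawal from data collection. Unless the subject withdraws consent, the site continues to time all cochlear implant appointments to 6 months and collects the 3- and 6-month outcomes where the subject is willing. The subject stays under the randomised arm. The investigator's health ground and the subject's right to withdraw remain as written. Nothing here bears on when the assigned model ought to be stopped, and the investigator's discretion need not be deleted.

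The cost is the amendment wording and a small change to the withdrawal form. Sites also take on continued timing, session-file transfer, speech testing and questionnaires for a few less cooperative subjects. These subjects have an implant and will probably still attend the clinic, so much of the timing can be done at visits that would happen anyway. The data will be noisier, and some outcomes will still be missing where the subject declines testing. The deviation form in section 8.3 already exists.

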9.3 Premature Study Termination

The Sponsor may terminate the study early in the case of major non-adherence to the protocol, or if it is anticipated that recruitment will not be met for the required number of subjects to complete the study objectives. In the event of premature study termination, the subjects who are already enrolled will be sponsored through study completion.

10. Data Analyses

10.1 Additional Analyses

- Evaluation of the number and reason for unscheduled visits outside new and traditional models and comparison between the models.
- Evaluation of (COSI) Client Oriented Scale of Improvement and Speech, Spatial, Qualities of Hearing Scale (SSQ-12) and relationship between the two measures.
- Evaluation of test administration between clinics.
- Observation of the number of subjects performing $\geq 20\%$ on CNC words pre to post at the 3-month interval for Group A and Group B.
- Evaluation of the communication documentation form to include comparison between Group A and Group B.

- Observation of the number of subjects performing $\geq 30\%$ on CNC words pre to post at the 6-month interval for Group A and Group B.
- Evaluation of clinic site differences in subject reported service satisfaction between sites and between and within Group A and Group B subjects.
- Evaluation of clinic site differences in time and outcomes between and within Group A and Group B.
- Evaluation of the effectiveness of self-guided subject materials for Group A subjects.

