psychoacoustic tests represent the auditory hierarchy skills. These include detection, discrimination, identification and comprehension of auditory stimulus. This technique can be utilized as a clinical tool for the audiologist to use in modifying programming parameters for both existing and newly implanted cochlear implant recipients. The AI technology is a tool used by an audiologist to provide programming modifications in a more consistent manner.

The AI system provides several recommendations to potentially improve outcomes, based on data across major cochlear implant systems and individual psychoacoustic data. These Artificial Intelligent recommendations can substantially reduce programming time, by reducing the overall number of programming visits, time taken within the visit, as well as assist the audiologist in implementing changes to the MAP based on evidence to a variety of parameters within the programming software for the average cochlear implant recipient (Battmer et al, 2015).

This system allows for test measures to be presented in a calibrated manner outside of the soundfield through the commercially available wired and wireless programming pods as compared to the traditional sound booth set-up which can be costly. There are several configurations which can be utilized based on clinician and patient preference as well as the sound processor type. One of these configurations is via the commercially available CP910 sound processor, Personal Audio Cable, and standard of care Cochlear Nucleus Programming Pod as shown in Figure 1 below. The software test module may allow for improved clinician and recipient experience by allowing the testing to be delivered directly to the recipient's sound processor outside of a sound booth.

Figure 1. Personal Audio Cable connection

[figure not shown]

Figure 2. AI system interaction

In addition, the evidence-based model provides recipient milestones based on a subjective outcome measure, Client Oriented Scale of Improvement (COSI). This enables the clinician to provide guidance and ways to track their progress during the aftercare process. The final component to the model is the structured use of materials and tools used to support the recipient in successfully using their device and related equipment. The model utilizes self-guided patient materials for device and accessory use.

4. Study Design Overview

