5.3.1.8 Materials/Tools Questionnaire

The in-house questionnaire will be completed by the professional to evaluate the subject's ability to complete basic device use and accessory use tasks at switch-on, 3 months and 6 months (Group A and B).

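### The last bullet of Section 10.1 frames the effectiveness of the self-guided materials as a Group A evaluation with no comparator, although the task questionnaire is scheduled in both randomised arms

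*Protocol*

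**What the plan says.** Self-guided materials belong to the new model. The Introduction (Section 3) says: "The model utilizes self-guided patient materials for device and accessory use". Under Section 5.4.3, Group A receives a take-home packet before switch-on and instructions for a support call, set for 2 weeks after activation. At switch-on (Section 5.5.1) Group A has "Self-directed device use using study materials and video conference call with Cochlear Recipient Services", while Group B has programming and counselling as each centre defines them. Accessory materials reach Group A at 1 month (Section 5.5.3) or, if not given then, at 3 months (Section 5.5.4).

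The instrument that rates task ability is the Materials/Tools questionnaire. Under Section 5.3.1.8 the professional completes it to "evaluate the subject's ability to complete basic device use and accessory use tasks at switch-on, 3 months and 6 months (Group A and B".

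Section 10.1 lists nine additional analyses. The last is "Evaluation of the effectiveness of self-guided subject materials for Group A subjects". Another bullet in the same list reads "Evaluation of the communication documentation form to include comparison between Group A and Group B".

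Secondary endpoint 3 in the synopsis (Section 1) is a between-arm statement: "Device and accessory use will be the same or better at 6 months of device use with the new model compared to the traditional model". It is measured by a device use questionnaire and datalogging.

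**The concern.** Effectiveness is a comparative claim. The relevant question is whether subjects who learn from self-guided materials handle their device and accessories as well as subjects counselled in the clinic's usual way. Group B supplies that comparison.

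A summary confined to Group A cannot answer it, because new users can be expected to become more able with practice whatever materials they receive. Nor does Group A have a rating from before the materials: Table 1 first marks the questionnaire at switch-on, after the take-home packet has been issued. A rise from switch-on to 6 months would therefore mix learning with later materials and clinic contact, and would miss whatever the packet had already achieved.

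The stake is modest but real. Time spent on accessories, device use and counselling counts towards appointment time (Section 4), and total appointment minutes are the primary endpoint. Evidence that self-learning left subjects no less able would help in interpreting any minutes saved.

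**Working it through.** **1. Which arms the bullets name.** Of the nine bullets in Section 10.1, six name both groups or both models: unscheduled visits, the two CNC improvement counts, the communication form, and the two on site differences. Two name no arm: COSI with SSQ-12, and test administration between clinics. Only the self-guided materials bullet names a single arm. In this list, naming groups generally says who is analysed, so the natural reading is a one-arm evaluation.

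**2. Whether comparator data are planned.**

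| Source | Materials/Tools questionnaire, Group B |
|---|---|
| Section 5.3.1.8 | switch-on, 3 and 6 months |
| Section 7, Table 2 | switch-on, 1, 3 and 6 months |
| Section 5.5.1 (switch-on list) | listed: "Complete Clinician reported Materials/Tools questionnaire" |
| Section 5.5.3 (1-month list) | not listed |
| Section 5.5.4 (3-month list) | not listed |
| Section 5.5.5 (6-month list) | not listed |

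The comparison is planned for, but a site working from the visit lists could miss the Group B ratings at 3 and 6 months. Table 1 likewise marks a 1-month rating for Group A that Sections 5.3.1.8 and 5.5.3 do not list.

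**3. How far learning alone could mislead.** The protocol states no figure to reproduce, so this is illustration only. Assumptions: 35 or 50 subjects in total (synopsis), 1:1 allocation (ratio not stated), two-sided 5% level, normal approximation, materials with no effect, and equal learning in both arms. Let L be the mean learning in SDs of change.

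The chance of a significant improvement within Group A is P = Φ(√nA × L − 1.96).

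| L | nA = 17 (total 35; 17.5 rounded down) | nA = 25 (total 50) |
|---|---|---|
| 0.25 | Φ(1.03 − 1.96) = 18% | Φ(1.25 − 1.96) = 24% |
| 0.5 | Φ(2.06 − 1.96) = 54% | Φ(2.50 − 1.96) = 71% |
| 0.8 | Φ(3.30 − 1.96) = 91% | Φ(4.00 − 1.96) = 98% |

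In a randomised A-versus-B comparison, equal learning cancels and the chance of a false result in favour of A is 2.5%, whatever L is.

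**4. What the randomised comparison can detect.** The difference detectable with 80% power is (1.96 + 0.84) × √(2/n), with n per arm:
- total 35, n = 17.5: 2.80 × 0.338 = 0.95 SD
- total 50, n = 25: 2.80 × 0.283 = 0.79 SD

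Only large differences are detectable, so the result should be read as an estimate with its interval.

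**The case against.** A reader might infer that the materials will be judged in Group A alone and that learning would be credited to them. The documents do not go that far. The bullet contains no word such as alone or only, names no instrument or time point, and describes no change from baseline. Naming Group A may merely identify who receives the materials. Section 6 sends statistical detail to a separate plan that is not shown, so the missing detail is not itself a fault. This stands: the supportable word is could. What remains is that the bullet, as worded, names one arm for an effectiveness claim where most of its neighbours name two.

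A reader might also infer that self-learning would be left with no controlled evidence. That is too strong. Secondary endpoint 3 compares device and accessory use between arms, and Section 10.1 compares unscheduled visits and communication forms, where failed self-learning could show. These fill the gap only in part. Endpoint 3 concerns use at 6 months, and the protocol does not say that its device use questionnaire is the Materials/Tools questionnaire, which rates task ability.

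Finally, A minus B does not isolate the materials. The arms also differ in AI programming, direct-connect testing, visit schedule and the video call. Nor can switch-on serve as the main time point for every task, since the support call and the accessory materials come later. Both points stand and shape the fix.

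**Conclusion.** The point holds as a minor one. As worded, the bullet invites a Group A-only evaluation in which ordinary learning could pass for an effect of the materials, while a randomised comparison on a scheduled instrument is available at almost no cost. It does not show that the sponsor intends an uncontrolled before-after test.

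The 18% to 98% range depends on the assumed amount of learning, 1:1 allocation and a significance test that the protocol does not specify. It shows the mechanism and does not predict this trial's result. The analysis is exploratory and leaves the primary and secondary endpoints unaffected. With 35 to 50 subjects the between-arm estimate will be imprecise, and a non-significant difference would not show equivalence. The conflict over Group B collection at 3 and 6 months is a matter of the text and needs no assumption.

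**What to change.** - Reword the last bullet of Section 10.1 so that this exploratory evaluation compares the Materials/Tools score between the arms as randomised, A minus B with a confidence interval. Use switch-on for basic device-use tasks and 3 and 6 months for accessory tasks. Where accessory materials are first given at the 3-month visit, 6 months is the more informative of the two.
- Label any Group A change over time as descriptive. Do not treat the switch-on rating as a baseline, since it follows randomisation and the take-home packet.
- Describe the contrast as the effect of the new-model package, not of the materials in isolation, and do not read non-significance as equivalence.
- Reconcile the Group B lists in Sections 5.5.4 and 5.5.5 with Section 5.3.1.8 and Table 2, so that the comparator ratings are collected. Reconcile the 1-month mark in Tables 1 and 2 with Sections 5.3.1.8 and 5.5.3.

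The cost is small wording changes in several sections and no data beyond what Section 5.3.1.8 already calls for. The price is an imprecise exploratory estimate.
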